3.4 Effectiveness measures

The effectiveness measure for the within-trial economic evaluation will be QALYs estimated from responses to the EQ-5D-5L data. The EQ-5D-5L measures health-related quality of life (HRQoL), which the National Institute of Health and Care Excellence (NICE) recommends. This general health questionnaire considers five domains, mobility, self-care, usual activities, pain/discomfort, and anxiety/ depression ⁽³¹⁾. Each of the five domains has five possible responses; there are, therefore, 3125 possible health states. These responses vary in severity from no, slight, moderate, severe, or extreme problems/inability to conduct usual activities). EQ-5D-5L values are converted into health state utility for each patient at each time point, estimated from a representative sample of the UK population ⁽³²⁾. This process is followed by mapping the EQ-5D-5L descriptive data set onto the EQ-5D-3L value set described in the NICE guidelines using the mapping/crosswalk algorithm⁽³¹⁾. Finally, we will conduct a sensitivity analysis to investigate the impact of using alternative crosswalk algorithms on the ICER results.

A proxy version of the EQ-5D-5L will be included for participants who cannot selfcomplete the questionnaires. EQ-5D–5L data will be collected at baseline, three, six and twelve months following randomisation. With the proxy version, the caregiver is asked to rate how they think the patient would rate their health-related quality of life if they could communicate. These responses will be converted into scores using population tariffs ⁽³¹⁾. The values from both participants and proxy values will be compared when both values are available to calculate QALY simultaneously. Following this, the variance between participant and proxy will be estimated. Where participant values are unavailable in the analysis, proxy values will be used.

The outcome data will then be converted into (QALYs) for each participant using the under-the-curve approach for baseline, three, six and twelve months. A QALY combines the quality of life and life expectancy into a single index ⁽³¹⁾. Standard deviations, standard errors and confidence intervals will be calculated using standard formulas for each of the mean utility measures. QALYs will be calculated by summing the area under the curve (AUC), connecting the mean utility measures at each time point for all three interventions. The AUC is calculated by summing up the areas of the shapes obtained from the linear relationship between utility scores during the study period ^(32,33).

CONFORM-OH HEAP Version 1.0 30th July 2023

Baseline means utility values may be imbalanced between treatment arms. Imbalanced utilities need to be considered when the mean differential QALYs are estimated. Estimation for mean differential QALYS can be achieved using multiple regression methods⁽³⁴⁾. This method controls for baseline utility values simultaneously, allowing for the Estimation of differential QALYs and the prediction of adjusted QALYS. The regression analysis provides unbiased estimates of differential QALYs between the trial's three arms, increasing the treatment effect's precision ⁽³⁵⁾.

3.5 Cost-utility analysis

The cost-utility analysis will base on the incremental cost per QALY gained and will be presented as the incremental cost-effectiveness ratio (ICER) and can be calculated by dividing the change of the expenses by the change in effect (QALYs). The total cost and QALY will be estimated for each arm, which will then be expressed as point estimates of the mean incremental costs and effects (QALYs) and the incremental cost per QALY gained. The UK's willingness to pay is approximately £20,000 per additional QALY; thus, if conservative management plus Fludrocortisone and conservative management plus Midodrine is not dominant, the ICER is within this threshold, the interventions could be deemed cost-effective by decision-makers. A dominant intervention is an intervention with a lower cost and better health outcomes than the comparator.

3.5.1 Adjusted analysis – seemingly unrelated regression (SUR)

Both unadjusted and adjusted analyses will be performed to estimate the costeffectiveness of conservative management plus Fludrocortisone compared to conservative management plus Midodrine compared to conservative management alone. The mean incremental costs, effects and cost-effectiveness results will be presented as point estimates.

An adjusted analysis will be carried out using seemingly unrelated regression (SUR) for all comments to estimate the costs and effects of the three interventions and their cost-effectiveness. SUR allows one to simultaneously estimate the costs and effects

CONFORM-OH HEAP Version 1.0 30th July 2023

for each individual, accounting for unobservable individual characteristics to affect both costs and effects, resulting in a potential correlation between two variables. Furthermore, the SUR permits the control for additional covariates such as age, baseline, severity and utility that could potentially affect costs and effects when appropriate. The covariates used in the SUR model will replicate the covariates used in the statistical analysis outlined in the Statistical Analysis Plan. We will analyse Stata using the seemingly unrelated regression command sureg (StataCorp LLC, Texas, USA).

3.5.2 Sensitivity analysis

A stochastic/probabilistic and deterministic sensitivity analysis will be conducted to characterise the uncertainty.

Stochastic sensitivity analysis

A stochastic sensitivity analysis will be conducted. Bootstrapping techniques will be utilised in this analysis ⁽³⁵⁾. (Bootstrapping can be described as the non-parametric technique used to estimate the distributions of important statistics relevant to the model, such as the ICER.⁽³⁶⁾. Stochastic analysis would explore the potential effects of statistical imprecision of parameters used within the model on costs effects and cost-effectiveness estimates if the sampling process could be repeated many times. Random values will be selected from the cost and QALY data retrieved from the trial. When a random value is used for the bootstrap resample, it is returned to the original sample. Consequently. A bootstrapped dataset derived from the complete case data on costs and outcomes from each trial arm.

This process will be carried out many times (e.g., 1000, 5000, 10,000), creating a sample of bootstrapped mean costs and QALYs with their corresponding distributions. The bootstrapped distribution will be calculated using bootstrapped costs, QALYS, and other parametric statistics. The results from the bootstrapping will be presented as a cost-effectiveness plane to demonstrate the distribution of incremental costs and incremental effects, allowing us to identify the distribution of total incremental costs and incremental effects. The horizontal axis will represent the QALYs difference between the two interventions, and the vertical axis will represent the corresponding cost difference. The bootstrapped results will also be presented

as cost-effectiveness acceptability curves (CEACs). CEACs enable us to identify the management strategy that maximises net benefits at each willingness to pay value for additional QALYs gained) ⁽³⁷⁾.

Deterministic sensitivity analysis

Deterministic sensitivity analysis will be used to assess the effect of assumptions such as dose of medications, method of conservative management and unit costs on the results using best-case and worst-case scenario analysis. A societal perspective will be used to explore the impact of patient costs on cost-effectiveness results. The results from the deterministic analysis will determine how the analysis will be performed, including one-way, two-way or multiway analysis.

To identify the primary inputs that could be changed to make Fludrocortisone and Conservative Management more or less cost-effective relative to both Midodrine and Conservative Management and Conservative Management alone.

Intervention costs

Conservative management

As mentioned before, we will use micro-costing to calculate conservative cost management. We will use sensitivity analysis to explore how low and high estimates affect the ICER. In addition, we will also investigate how the type of conservative management can influence the ICER separately. This form of analysis will be achieved by one-way sensitivity analysis. We will use higher and lower values of the intervention cost using a 95% confidence interval. Multiway sensitivity analysis will allow us to assess the impact of variation in the costs of Fludrocortisone and Midodrine.

Fludrocortisone and Midodrine

As mentioned, certain assumptions about the pharmacological interventions, such as the dose strength and the number of tablets used in a day, will be tested using sensitivity analysis. In the sensitivity analysis, we will explore the effect of each medication's high and low estimations on the ICER.

Cost of services

As mentioned previously, the assumptions about the cost of services would be assessed using sensitivity analysis. This analysis will determine non-NHS, private healthcare, and social care resources. For each cost, we will investigate the effect of using higher and lower cost estimates on the cost-effectiveness results, and whether the ICER goes above or below the threshold. Results from the sensitivity analysis will be presented using a tornado diagram for multiple one-way sensitivity analyses for higher and lower values of service cost.

Utility values

We will use EQ-5D-5L crosswalked to the EQ-5D-3L value set in the base case analysis ⁽³¹⁾. In sensitivity analyses, we will use alternative crosswalk algorithms (e.g., provided by van Hout et al.) and the population value set for the EQ-5D-5L to investigate the effect of these utility values on the ICER⁽³⁸⁾.

In a further sensitivity analysis, proxy values based on the degree of discordance between participants and the proxy values will be used in the sensitivity analysis. The reported proxy values will be replaced with alternative values estimated by converting the upper and lower confidence intervals of a paired t-test. This will compare the patient and proxy values into a % variation from the man score by applying that % variation of the observed score. This will mean that high and low values utilised in the sensitivity analysis will be a proxy score * (1+ x) or proxy score * (1-x), when x is the % variation.

Total costs and utility

To deal with missing costs and utility data, we will do multiple imputations in the sensitivity analysis. An ICER will be presented in addition to the base case analysis.

3.6 Handling Missing Data

Potential issues may arise when dealing with trial data, such as missing data and not adhering to the protocol. Therefore, a missing data analysis will be carried out.

This missing data analysis will primarily focus on missing data because the e-CRF and participant questionnaires are incomplete. As with most trial-based data collection, not all participants who enter the trial will complete all questionnaires and questions in each questionnaire. Therefore, missing data is expected. When we have a full trial dataset available, the imputation methods will be determined as the most appropriate, depending on the nature of the missing data.

4. Close Down Plan

4,1 Summary of Existing Economic Component

The health economics component for CONFORM-OH,-, had it been recruited to target, would have included a within-trial cost-utility analysis with longer-term model-based extrapolation. For both the within-trial and model-based analysis, the results will be reported as incremental costs, QALYs, and incremental costs per QALY gained.

The within-trial analysis cost and outcomes for the three trial intervention arms would have been based on data collected over the 12-month follow-up period. Costs were to fall on the NHS, personal social services (PSS), participants and their families. These costs were to be based upon the use of health and social services and, as part of the costs falling on patients and their families, the time and travel costs of accessing services. QALYs were to be based upon responses to the EQ-5D-5L collected from participants at baseline, three, six and 12 months.

The plan was also to use an economic model to extrapolate outcomes into the longer term. Outcomes of the model will be expressed in terms of costs to the NHS and PSS, QALYs, and incremental cost per QALY gained. The model will be structured as when there is a choice about whether or not to start medical treatment and which

medical treatment to start, and it would follow individuals for the remainder of their life. The model was to be developed per the NICE reference case ⁽³⁹⁸⁾.

4.2 Close-down Plan

Given the likely data available from the trial, we no longer propose to conduct a complete within-trial economic evaluation of the model-based analysis. As an alternative, we will use the available trial data to:

 Provide descriptive statistics (e.g. mean, medians and appropriate measures of variance around completion rates for each health economic data collection tool (i.e. the health service utilisation questionnaire and EQ-5D-5L completed at baseline, 3, 6, 12 months)

2) Provide descriptive statistics (e.g. mean, medians and appropriate measures of variance) for each area of resource use collected at each time point and overall as part of the trial and by group.

3) Provide descriptive statistics for the EQ-5D-5L utility score and EQ-5D-VAS (e.g. mean, medians and appropriate measures of variance) at each time point and overall as part of the trial overall and by group.

4) For each trial respondent, map changes by level on the EQ-5D-5L descriptive framework for responses to the EQ-5D-5L at baseline, 3 and 6 months. There will be insufficient data at 12 months to make a similar work useful.

Analyses 1-3 are consistent with the work proposed in Section 3 of the Health Economic Analysis Plan, Version 0.2. These analyses will provide information for any subsequent evidence synthesis project (e.g., a systematic review or modelling exercise). The data will also help plan future evaluations addressing the same or similar research questions. Specifically, question 1 will provide some information as to whether the tools used can be completed by this group of people (or their proxies). Question 2 will illustrate where resources are used, which may help design future data collection tools that balance data collection against respondent burden. Questions 3 and 4 will help inform whether the EQ-5D-5L can detect any changes in health status in this group of people.

CONFORM-OH HEAP Version 1.0 30th July 2023

In addition to the above, we propose using the data from the trial assembled from the literature and expert opinion to conduct an early economic evaluation model. This approach is used in other healthcare contexts to help design future primary research. This element aims to identify key uncertainties and estimate, using the methods of Value of Sample Information, the sample size required for a definitive trial to address the research question. Expected value of information will be calculated.

5. References

6.1.1 Education intervention

6.1.1.1 staff

Staff		Time involved	Cost per	Cost per consultations	Number of Consultations	Total staff	Notes
Туре	Grade		minute			costs*	
Staff member 1							
Staff member 2							
Totals							

* These are calculated

6.1.1.2 Overheads

Overhead type	Unit cost	Cost per session*	Number of sessions*	Total overhead costs*	Note
Туре	Cost per minute				
Room cost					
Heat power and light					
Internet					
Print outs					
Totals					

* These are calculated

6.1.1.3 equipment disposable

Equipment item		Cost per item	Cost per session*	Number of sessions	Total Equipment
Туре	Number used				costs*
Equipment 1					
Equipment 2					
Totals					

6.1.1.4 equipment reusable

Equipment item/Type	Number used	Number of times equipment can be used	Lifespan (years)	Discount rate	Cost per item per use	Cost per session*	Number of sessions*	Total reusable Equipment costs*
Equipment 1								
Equipment 2								
Totals								

6.1.2 Trigger avoidance

6.1.2.1 staff

Staff		Time involved	Cost per	Cost per Consultations	Number of Consultations	Total staff	Notes
Туре	Grade		minute			costs*	
Staff member 1							
Staff member 2							
Totals							

6.1.2.2 Overheads

Overhead type	Cost per minute	Cost per session*	Number of sessions*	Total overhead costs*
Room cost				
Heat power and light				
Internet				
Print outs				
Totals				

* These are calculated

6.1.2.3 equipment disposable

Equipment item		Cost per item	Cost per session*	Number of sessions	Total Equipment
Туре	Number used				costs*
Equipment 1					
Equipment 2					
Totals					

6.1.2.4 equipment reusable

Equipment	Number	Number of	Lifespan	Discount	Cost	Cost per	Number	Total
item	used	times	(years)	rate	per	session*	of	reusable
		equipment			item		sessions*	Equipment
		can be			per			costs*
		used			use			
Equipmont								
1								
1								
Equipment								
2								
lotals								

6.1.3 Safe Standing

6.1.3.1 staff

Staff		Time involved	Cost per minute	Cost per Consultations	Number of Consultations	Total staff
Туре	Grade					costs*
Staff member 1						
Staff member 2						
Totals						

* These are calculated

6.1.3.2 Overheads

Overhead type	Cost per	Cost per	Number of	Total	Notes
	minute	session*	sessions*	overhead	
				costs*	
Room cost					
Heat power and light					
Internet					
Print outs					
Totals					

* These are calculated

6.1.3.3 equipment disposable

Equipment item		Cost per item	COST PER	Number of	Total
			SESSION*	sessions	Equipment
Туре	Number				costs*
	used				00010
Equipment 1					
Equipment 2					
Totals					

6.1.3.4 equipment reusable

Equipment item	Number used	Number of times equipment can be used	Lifespan (years)	Discount rate	Cost per item per use	Cost per session*	Number of sessions*	Total reusable Equipment costs*
Equipment 1								
Equipment 2								
Totals								

6.1.4 Physical counter-manoeuvre

6.1.4.1 staff

Staff		Time involved	Cost per minute	Cost per Consultations	Number of Consultations	Total staff
Туре	Grade					costs*
Staff member 1						
Staff member 2						
Totals						

* These are calculated

6.1.4.2 Overheads

Overhead type	Cost per	Cost per	Number of	Total
	minute	session *	sessions*	overhead
				costs*
Room cost				
Heat power and light				
Internet				
Print outs				
Totals				

* These are calculated

6.1.4.3 equipment disposable

Equipment item		Cost per item	Cost per session*	Number of sessions	Total Equipment costs*
Туре	Number used				
Equipment 1					
Equipment 2					
Totals					

CONFORM-OH HEAP Version 1.0 30th July 2023

6.1.4.4Equipment reusable

Equipment item	Number used	Number of times equipment can be used	Lifespan (years)	Discount rate	Cost per item per use	Cost per session*	Number of sessions*	Total reusable Equipment costs*
Туре								
Equipment 1								
Equipment 2								
Totals								

6.1.5 Fluid and salt intake

6.1.5.1Staff

Staff		Time involved	Cost per minute	Cost per consultations	Number of Consultations	Total staff
Туре	Grade					costs*
Staff member 1						
Staff member 2						
Totals						

* These are calculated

6.1.5.2 Overheads

Overhead type	Cost per minute	Cost per session*	Number of sessions*	Total overhead costs*
Room cost				
Heat power and light				
Internet				
Print outs				
Totals				

* These are calculated

6.1.5.3 equipment disposable

Equipment item		Cost per item	Cost per session*	Number of sessions	Total Equipment costs*
Туре	Number used				
Equipment 1					
Equipment 2					
Totals					

CONFORM-OH HEAP Version 1.0 30th July 2023

6.1.5.4 equipment reusable

Equipment item	Number used	Number of times equipment can be used	Lifespan (years)	Discount rate	Cost per item per use	Cost per session*	Number of sessions*	Total reusable Equipment costs*
Equipment 1								
Equipment 2								
Totals								

6.1.6 Compression hosiery

6.1.6.1 staff

Staff		Time	Cost per	Cost per	Number of	Total
		involved	minute	Consultations	Consultations	staff
Туре	Grade					costs*
Staff member						
1						
Staff member						
2						
Totals						

* These are calculated

5.1.6.2 Overheads

Overhead type	Cost per	Cost per session*	Number of	Total overhead
Overhead type	0031 pci	0031 per 30331011		Total overhead
	minute		sessions*	costs*
Room cost				
Heat power and				
light				
iigint				
Internet				
Print outs				
Finit Outs				
Totals				

6.1.6.3 equipment disposable

Equipment item		Cost per item	Cost per	Number of	Total
			session*	sessions	Equipment
_	T				costs*
Туре	Number				
	used				
Equipment					
1					
Equipment					
2					
Totals					

6.1.6.4Equipment reusable

Equipment	Number used	Number of	Lifespan (years)	Discount rate	Cost per	Cost per	Number of	Total reusable
item		times			item per	session*	sessions*	Equipment costs*
		equipment can			use			
		be used						
Equipment 1								
Equipment 2								
Totals								

6.2 Pharmacological interventions

6.2.1 Fludrocortisone

Staff	Grade	Time	Cost	Cost per	Number	Total staff
Administering		involved	per	Session	of	costs*
Fludrocortisone			minute		sessions	
Staff Member 1						
Staff Member 2						
Total						

CONFORM-OH HEAP Version 1.0 30th July 2023

6.2.2 Cost of medications

Dose in	Strength of tablet	Cost per	Number of	Frequenc	Cost per	Number of	Total	Time	Total
Protocol	according to BNF	pack	tablets per	y per day	tablet £	tables used	cost	horizon in	Costs
			pack			per dose	per	days	
							day		
Typical dose	100 micrograms	£8.06	30	1	£0.27	1	£0.27	365	£98.06
is 100									
micrograms									
Starting dose	100 micrograms	£8.06	30	1	£0.27	0.5	£0.13	365	£49.03
50									
micrograms									
Maximal	100 micrograms	£8.06	30	1	£0.27	3	£0.81	365	£294.19
dose of 300									
micrograms									

6.2.3 Midodrine

Staff	Grade	Time	Cost per	Cost per	Number	Total staff
Administering		involved	minute	session*	of	costs *
Fludrocortisone					sessions	
Staff Member 1						
Staff Member 2						
Total						

CONFORM-OH HEAP Version 1.0 30th July 2023

6.2.4 Medications

Dose in	Strength	Cost per	Number	Frequency	Cost	Number	Total	Number	Total
Protocol	of tablet	pack	of	per day	per	of tables	cost	of days	Costs*
	according		tablets		tablet	used per	per day		
	to BNF		per		£	dose			
			pack						
The									
typical									
starting									
dose is									
2.5mg									
Maximum									
dose									
10mg									

6.3 Healthcare Resources

6.3.1 National Health Care Service

Resource	Mean length of consultation in minutes	Number of appointments	Cost per minute	Cost per Consultation	Total staff cost*	Source /Notes
GP at Practice	9.22		£4.23	£39.00		42 weeks per year. 41.4 hours per week, including direct staff costs with qualifications PSSRU 2019/20
GP on Phone	4		£3.88	£15.520		44 weeks per year, 41.7 hours per week PSSRU 2019/20, including other costs per year
Nurse at GP practice	NA		£0.73	£44		41.9 weeks per year 37.5 hours per week costs including qualifications PSSRU 2019/20,44 per hour
Nurse on the Phone	6.56		£1.19	£7.80		42 Weeks per year, 37.5 hours per week

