3.3.3 Costs of NHS Resources

During the following-up period, participants may utilise additional healthcare resources. Examples of Primary care resources can include GP, nurse/or other healthcare professional consultations. Primary care consultations can occur in various places, healthcare providers' various places, healthcare providers' various places, healthcare providers' practices, the participant's home, and over the telephone (including phone calls to NHS call centres). Secondary care resource use can refer to A and E departments, outpatient visits, and hospital admissions, which could be a day or overnight.

The Health Utilisation Questionnaires are used to capture the use of primary care services, including the number of contacts with GP, nurses, and " other health professionals" "". We aim to capture all potential forms of primary care costs were captured. For example, primary care consultations may be face-to-face at the practice, at the " 'participant's home, or by telephone. The differentiation is important as the cost of each of these varies (see below on derivation of unit costs). Secondary

care refers to visits to an A & E department, outpatient clinics and hospital admissions as a day patient or as an inpatient (inpatient admissions are defined as where the person stays at least one night in the hospital).

Healthcare resource use is associated with different unit costs, regardless of whether these resources are primary or secondary. Details of resource use of primary and secondary care will be captured using the e-CRF and follow-up Health Utilisation Questionnaires at baseline, three months, six months, and 12 months after the trial. The dummy tables used to estimate these costs are shown in the Appendix, Table 5.3.

The number of face-to-face or phone appointments with their GP or nurse within a specific time horizon will be extracted from the e-CRF. The cost per minute and the mean length of consultation in minutes can be removed from the Unit cost of health and Social Care ⁽¹⁵⁾. The costs per consultation will be multiplied by the number of appointments within a time horizon to calculate the total staff costs per patient for each patient, thus allowing us to calculate the average staff per patient for each intervention arm. The dummy tables used to estimate these costs are shown in the Appendix, Table 5.3.

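### SAP table 6.3.1 enters the practice nurse's hourly rate (£44) as the cost of one face-to-face consultation

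*SAP*

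**What the plan says.** Section 3.3.3 of the SAP sets out how GP and nurse contacts are to be costed. Two inputs come from the national unit-cost source: "The cost per minute and the mean length of consultation in minutes". The resulting price is then scaled up by use: "The costs per consultation will be multiplied by the number of appointments within a time horizon". The section sends the reader to the appendix tables for these calculations.

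Table 6.3.1 holds the prices. Most appendix tables are blank, but the unit-cost cells here are filled in, apart from one length. The columns are length in minutes, number of appointments (blank), cost per minute and cost per consultation:

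- "GP at Practice 9.22 £4.23 £39.00"
- "GP on Phone 4 £3.88 £15.520"
- "Nurse at GP practice NA £0.73 £44"
- "Nurse on the Phone 6.56 £1.19 £7.80"

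The note beside the third row reads in part: "costs including qualifications PSSRU 2019/20,44 per hour".

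Section 4.2, written after the early closure, limits what will be done: "we no longer propose to conduct a complete within-trial economic evaluation". It keeps descriptive summaries of resource use and EQ-5D-5L, and adds an early economic model with a value-of-information analysis.

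**The concern.** The face-to-face nurse row is the only one of the four without a length, and the only one whose consultation price cannot be built from its own inputs. The price shown equals the hourly figure in the note, so a rate per hour appears to sit in a column of prices per visit.

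If the table is used as section 3.3.3 directs, every face-to-face practice-nurse visit is priced as a visit of about an hour. The error always runs upwards for visits shorter than an hour, and it multiplies with the number of visits. Any difference between arms in these visits would be inflated by the same factor. An economic model that took its price from this table would inherit the error.

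**Working it through.** **Inputs.** All come from table 6.3.1: minutes, rate per minute and price per consultation for each of the four rows, plus the hourly figure in the note to the practice-nurse row.

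**Step 1: reproduce the table.** Rule from section 3.3.3: price per consultation = minutes x rate per minute.

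| Row | Minutes x rate | Result | Stated |
|---|---|---|---|
| GP at practice | 9.22 x £4.23 | £39.00 | £39.00 |
| GP by telephone | 4 x £3.88 | £15.52 | £15.52 |
| Nurse by telephone | 6.56 x £1.19 | £7.81 | £7.80 |
| Nurse at practice | NA x £0.73 | cannot be formed | £44 |

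Three rows follow the rule, to within a penny. The fourth does not.

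**Step 2: identify the £44.** £44 / 60 = £0.733, which rounds to the row's £0.73 per minute. In reverse, £0.73 x 60 = £43.80. Read as a price per visit, £44 implies £44 / £0.73 = 60.3 minutes.

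**Step 3: compare with the GP row.** £44 / £39.00 = 1.13, so the nurse visit is priced 13% above the GP visit. Yet £0.73 / £4.23 = 0.17, so a nurse minute costs about one sixth of a GP minute.

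**Step 4: size of the overcosting.** Factor = £44 / (£0.73 x length), which is close to 60 / length. The SAP states no length for a face-to-face nurse visit, so every length below is an assumption. Two are borrowed from other rows (6.56 minutes from the nurse telephone row, 9.22 from the GP row); the rest are illustrative.

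| Assumed minutes | Price at £0.73 per minute | £44 divided by that price |
|---|---|---|
| 6.56 | £4.79 | 9.2 |
| 9.22 | £6.73 | 6.5 |
| 10 | £7.30 | 6.0 |
| 15 | £10.95 | 4.0 |
| 20 | £14.60 | 3.0 |
| 30 | £21.90 | 2.0 |

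**Step 5: sensitivity to the rate.** The same table uses £1.19 per minute for a nurse on the telephone and does not say why this differs from £0.73. At £1.19, visits of 6.56 and 15 minutes would cost £7.81 and £17.85, and £44 would be 5.6 and 2.5 times those prices. Even at that rate £44 implies £44 / £1.19 = 37 minutes.

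**The case against.** The strongest reply is that nothing still planned is shown to use this cell. Section 2 says that section 3 records the analysis as first planned and that section 4 governs after the early closure. Section 4.2 drops the complete evaluation. Its resource-use item can be met with counts, which no price affects. For the early model it mentions trial data, literature and expert opinion, and does not name the appendix tables. All of this stands, and it lowers the severity. It does not make the figure correct, and this table is where the SAP states a price for a practice-nurse visit.

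A second reply is that the written method is right and the row is visibly unfinished: the length reads NA, the note says the figure is hourly, and the appendix is headed as dummy tables. That is fair, but this cell is filled with a number that can be used as it stands. Section 3.3.7 does plan high and low estimates for each cost input; these would vary around a wrong base value without repairing it.

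Three stronger readings are tempting, and the document does not support them:

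- A reader might take a 4- to 9-fold overcosting as established. That range needs visits of about 6.6 to 15 minutes. The lower end is a telephone length, and the upper end is not in the SAP.
- A reader might extend the error to all nurse contacts. The telephone row agrees with its own inputs.
- A reader might infer that the comparison between arms is distorted by a known amount. The SAP gives no visit counts by arm. Equal mean use in the arms would cancel in the cost difference, so a per-patient excess built on an invented number of visits says nothing about incremental cost.

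**Conclusion.** The figure is wrong as written. That £44 is an hourly rate in a per-visit column follows from the row itself, its note and the pattern of the other rows, with no outside source. Used as section 3.3.3 directs, it charges a face-to-face practice-nurse visit as about 60 minutes.

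The direction is certain for any visit under an hour. The size depends on a length the SAP does not give: 2.0 to 9.2 times too high for assumed visits of 30 down to 6.56 minutes at the row's own rate.

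Severity is moderate to minor. The consequence is conditional on the price being used in the early economic model or in some other costing.

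**What to change.** Before any costing or modelling draws on table 6.3.1:

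1. Replace NA in the practice-nurse row with a sourced mean consultation length. If none is found, state an assumed length and show results over a range.
2. Set the price per consultation to that length multiplied by the rate per minute, as in the other rows.
3. Keep £44 only in the note, as the hourly rate.
4. State why the nurse rate per minute is £0.73 at the practice and £1.19 on the telephone, or align the two.
5. While the row is open, reconcile the price year: its note cites the 2019/20 unit costs, whereas reference 15 in the text is the 2021 edition.

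The cost is one table row and its note. No new trial data are needed, but the consultation length has to come from a source outside the SAP or be declared as an assumption.
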